### **Portal Vein Thrombosis**

Transplanted islets release tissue factor and exhibit prothrombotic properties when infused to an intravascular site such as the portal vein. A partial portal vein thrombosis has been reported in one of six patients transplanted at the intramural National Institutes of Health (NIH) program^76. In the Edmonton single-center experience, the risk of partial vein thrombosis was 3% in more than 100 intraportal islet transplants. The management of partial vein thrombosis includes anticoagulation therapy which may lead to intra-abdominal hemorrhage requiring transfusion and surgical intervention. There is one published report of complete thrombosis of the portal vein thrombosis after transplantation of partially purified pancreatic islets in a combined islet/liver allograft, which necessitated emergency re-transplantation of the liver. This complication probably related to the transplantation of partially purified islet tissue derived from 4 donors into a freshly transplanted liver. A right upper quadrant ultrasound including Doppler examination of the portal vein is performed on islet transplant recipients on days 1 and 7 post-transplant. Early diagnosis and prompt management of branch vein portal occlusion with systemic heparinization may prevent clot propagation. Repeated intraportal islet transplants are generally contraindicated in patients that have experienced prior portal thrombus.

### **Injuries to Other Structures**

One instance of gall bladder perforation during percutaneous transhepatic catheterization of the portal vein requiring laparoscopic cholecystectomy has been reported to the Islet Transplant Registry. Acute cholecystitis, possibly related to percutaneous transhepatic catheterization of the portal vein, has been noted in 2 of the 86 islet allograft recipients reported to CITR^74. Gall bladder hematoma (n=1) and gall bladder opacification (n=2) have been observed as well.

#### **1.5.4.4 FOLLOW-UP PROCEDURES**

### **Glomerular Filtration Rate (GFR)**

Risks associated with the GFR procedure are minimal and are related to the blood draw process. Rarely, the following will occur: excessive bleeding at blood draw site, syncope, extravasation of injection, hematoma, or infection. Iohexol has been widely used and has an excellent safety record. Very occasionally, allergic reactions to iohexol may occur.

### 1.5.5 Benefits

#### 1.5.5.1 BENEFITS OF ALLOGENIC ISLET TRANSPLANTATION

Successful islet transplantation alleviates T1D patients from life-threatening hypoglycemia and psychosocially debilitating glycemic lability. While the long-term durability of these responses is at present uncertain, they persist for as long as some graft function is maintained, despite the eventual return to insulin therapy in the majority of recipients. This partial function, as indicated by continued c-peptide production, may be present in as many as 80% of recipients after 5 years. Furthermore, as long as graft function is maintained, fear of hypoglycemia and anxiety are significantly lower after islet transplantation. Indeed, T1D subjects in the DCCT who had persistent c-peptide production had a significantly reduced risk of severe hypoglycemia despite intensive insulin therapy. Additionally, while most transplant recipients experience only a temporary reprieve from exogenous insulin therapy, a few have maintained insulin-independent graft function for more than 3 years. Novel strategies aimed at promoting the engraftment or survival of transplanted islets may lead to improved long-term graft function and further the duration of insulin-independence after transplantation, and hopefully lead to reductions in the secondary complications of T1D.

#### 1.5.5.2 BENEFITS OF STUDY REGIMEN

Potential benefits of a belatacept regimen include avoidance of tacrolimus-related side effects, such as nephrotoxicity, hypertension, dyslipidemia, and glucose intolerance, avoidance of sirolimus-related toxicity such as buccal ulcers and dyslipidemia, and minimization of the risk of procedure related AEs if a higher frequency of success with islet transplantation using islets from single donors is achieved by avoidance of tacrolimus and sirolimus.

Tacrolimus is known to be directly beta-cell toxic in vitro and in vivo, and has been associated with new onset immunosuppression-related diabetes in non-diabetic recipients of solid organ transplants. Islet transplants may be particularly sensitive to early exposure to calcineurin inhibitors (CNI's), as intraportally delivered islets are exposed to high peak levels of CNI's when given orally and absorbed via the portal vein. The current protocol also eliminates exposure to sirolimus. Sirolimus may have a negative impact on islet neovascularization and engraftment. For these reasons we hypothesize that the proposed trial will optimize early islet engraftment and function, as well as minimizing risk of islet allograft rejection or autoimmune recurrence.

## **2. OBJECTIVES**

### **2.1 Primary Objective**

The primary objective of this protocol is to assess the safety and efficacy of an immunosuppressive medication consisting of a monoclonal antibody IL-2 receptor blocker (basiliximab), belatacept and mycophenolate mofetil in islet transplantation. The primary efficacy measure will be the proportion of insulin-independent subjects at day 75 ( $\pm$  5 days) following the first islet transplant.

### **2.2 Secondary Objectives**

The secondary objective is to assess islet graft function in the absence of calcineurin inhibitor drugs, with determination of success being the proportion of patients attaining and maintaining insulin independence after receiving a maximum of 3 islet transplants.

Additional objectives are to obtain samples for the islet and immune function mechanistic studies which are described in Section 9.

### 3. SELECTION OF SUBJECTS

#### 3.1 Inclusion Criteria

Patients who meet all of the following criteria are eligible for participation in the study:

1. Male and female patients age 18 to 65 years of age.
2. Ability to provide written informed consent.
3. Mentally stable and able to comply with the procedures of the study protocol.
4. Clinical history compatible with T1D with onset of disease at < 40 years of age, insulin-dependence for  $\geq 5$  years at the time of enrollment, and a sum of patient age and insulin dependent diabetes duration of  $\geq 28$ .
5. Absent stimulated c-peptide ( $<0.3\text{ng/mL}$ ) in response to a mixed meal tolerance test (MMTT; Boost® 6 mL/kg body weight to a maximum of 360 mL; another product with equivalent caloric and nutrient content may be substituted for Boost®) measured at 60 and 90 min after the start of consumption.
6. Involvement in intensive diabetes management defined as self monitoring of glucose values no less than a mean of three times each day averaged over each week and by the administration of three or more insulin injections each day or insulin pump therapy. Such management must be under the direction of an endocrinologist, diabetologist, or diabetes specialist with at least 3 clinical evaluations during the 12 months prior to study enrollment.
7. At least one episode of **severe hypoglycemia** in the 12 months prior to study enrollment.
8. Reduced awareness of hypoglycemia as defined by a Clarke score of 4 or more OR a HYPO score greater than or equal to the 90th percentile (1047) during the screening period and within the last 6 months prior to randomization;

**OR**

Marked glycemic lability characterized by wide swings in blood glucose despite optimal diabetes therapy and defined by a LI score greater than or equal to the 90th percentile ( $433 \text{ mmol/L}^2/\text{h wk}^{-1}$ ) during the screening period and within the last 6 months prior to randomization;

**OR**

A composite of a Clarke score of 4 or more and a HYPO score greater than or equal to the 75th percentile (423) and an LI greater than or equal to the 75th percentile (329) during the screening period and within the last 6 months prior to randomization.

### 3.2 Exclusion Criteria

Patients who meet any of these criteria are not eligible for participation in the study:

1. Body mass index (BMI)  $>30$  kg/m^2 or patient weight  $\leq 50$ kg.
2. Insulin requirement of  $> 1.0$  IU/kg/day or  $<15$  U/day.
3. HbA1c  $>10\%$ .
4. Untreated proliferative diabetic retinopathy.
5. Blood Pressure: SBP  $> 160$ mmHg or DBP  $> 100$ mmHg.
6. Measured glomerular filtration rate (using iohexol) of  $<80$  mL/min/1.73m^2 (or for subjects with an iodine allergy, calculated using the subject's measured serum creatinine and the Chronic Kidney Disease Epidemiology Collaboration (CKD-EPI) equation). Strict vegetarians (vegans) with a calculated GFR  $< 70$  mL/min/1.73m^2 are excluded. The absolute (raw) GFR value will be used for subjects with body surface areas  $> 1.73$  m^2.
7. Presence or history of macroalbuminuria ( $>300$ mg/g creatinine).
8. Presence or history of panel-reactive anti-HLA antibodies above background by flow cytometry.
9. For female subjects: a) Positive serum pregnancy test (minimum sensitivity 25 IU/L or equivalent units of human chorionic gonadotropin [HCG]) within 72 hours prior to the start of study medication; b) presently breast-feeding; c) unwillingness to use effective contraceptive measures to avoid pregnancy in such a manner that the risk of pregnancy is minimized for the duration of the study and 4 months after discontinuation. For male subjects: intent to procreate during the duration of the study or within 4 months after discontinuation or unwillingness to use effective measures of contraception. All participants must use two acceptable methods of contraception while taking mycophenolate mofetil (MMF). For females of child bearing potential, the two methods should be started 4 weeks prior to the first dose of MMF. Oral contraceptives, Norplant®, Depo-Provera®, and barrier devices with spermicide are acceptable contraceptive methods; condoms used alone are not acceptable.
10. All women  $\geq 35$  years and women of any age who have first degree relatives with a history of breast carcinoma, or who have other risk factors of breast carcinoma, must have a screening mammogram, or provide results of a screening mammogram performed within 6 months of enrollment. Subjects with a mammogram that is suspicious for malignancy and in whom the possibility of malignancy cannot be reasonably excluded following additional clinical, laboratory, or other diagnostic evaluations will be excluded.
11. Active infection including hepatitis B, hepatitis C, or HIV.
12. Presence or history of active tuberculosis (TB). Subjects with laboratory evidence of active infection are excluded even in the absence of clinical evidence of active infection.
13. Negative screen for Epstein-Barr Virus (EBV) by IgG determination.

14. Invasive aspergillus, histoplasmosis, or coccidioidomycosis infection within one year prior to study enrollment.
15. Any history of malignancy except for completely resected squamous or basal cell carcinoma of the skin.
16. Known active alcohol or substance abuse.
17. Baseline Hb below the lower limits of normal at the local laboratory; lymphopenia ( $<1,000/\mu\text{L}$ ), neutropenia ( $<1,500/\mu\text{L}$ ), or thrombocytopenia (platelets  $<100,000/\mu\text{L}$ ). Participants with lymphopenia are allowed if the investigator determines there is no additional risk and obtains clearance from an independent hematologist.
18. A history of Factor V deficiency.
19. Any coagulopathy or medical condition requiring long-term anticoagulant therapy (e.g., warfarin) after islet transplantation (low-dose aspirin treatment is allowed) or patients with an International normalized ration (INR)  $>1.5$ . The use of Plavix is allowed only when portal vein access is obtained using a mini-laparotomy procedure at the time of islet transplant.
20. Severe co-existing cardiac disease, characterized by any one of these conditions:
  - a) Recent myocardial infarction (within past 6 months).
  - b) Evidence of ischemia on functional cardiac exam within the last year.
  - c) Left ventricular ejection fraction  $<30\%$ .
21. Persistent elevation of liver function tests at the time of study entry. Persistent serum glutamic-oxaloacetic transaminase (SGOT [AST]), serum glutamate pyruvate transaminase (SGPT [ALT]), Alk Phos or total bilirubin, with values  $>1.5$  times normal upper limits will exclude a patient. Known cirrhosis of the liver or portal hypertension.
22. Symptomatic cholelithiasis.
23. Acute or chronic pancreatitis.
24. Symptomatic peptic ulcer disease.
25. Severe unremitting diarrhea, vomiting or other gastrointestinal disorders potentially interfering with the ability to absorb oral medications.
26. Hyperlipidemia despite medical therapy (fasting low-density lipoprotein [LDL] cholesterol  $> 130$  mg/dL, treated or untreated; and/or fasting triglycerides  $> 200$  mg/dL).
27. Receiving treatment for a medical condition requiring chronic use of systemic steroids except for the use of  $\leq 5$  mg prednisone daily, or an equivalent dose of hydrocortisone, for physiological replacement only.
28. Treatment with any anti-diabetic medication other than insulin within 4 weeks of enrollment.
29. Use of any other investigational agents within 4 weeks of enrollment.
30. Subjects previously treated with belatacept.

[figure not shown]
31. Administration of live attenuated vaccine(s) within 2 months of enrollment.
32. Any medical condition that, in the opinion of the investigator, will interfere with safe participation in the trial.
33. Prisoners or subject who are compulsorily detained (involuntarily incarcerated) for treatment of either a psychiatric or physical (e.g., infectious disease) illness.
34. Treatment with any immunosuppressive regimen at the time of enrollment, or subjects with comorbidities for which treatment with such agents are likely during the trial.
35. A previous islet transplant.
36. A previous pancreas transplant, unless the graft failed within the first week due to thrombosis, followed by pancreatectomy and the transplant occurred more than 6 months prior to enrollment.
37. Known hypersensitivity to mycophenolate mofetil or any of the drug's components.
38. Rare hereditary deficiency of hypoxanthine-guanine phosphoribosyltransferase (HGPRT) such as Lesch-Nyhan and Kelly-Seegmiller syndrome.
39. Dietary restriction of phenylalanine.

## 4. STUDY DESIGN

This trial is a prospective, two-center, open-label, pilot study of islet transplantation assessing the safety and efficacy of a steroid-free, calcineurin inhibitor-free belatacept based immunosuppressive medication in subjects with long-standing T1D that is refractory to intensive insulin therapy. The two centers participating in this phase 2 study will also undertake a separate, phase 3 study in islet transplantation, using a standard manufacturing and immunosuppressive regimen. The phase 3 trial, Protocol CIT07, will have inclusion/exclusion criteria and endpoint measures that are identical to those in this phase 2 trial. In order to avoid bias in selection of subjects, eligible subjects will be randomized, prior to transplantation, to participate either in this phase 2 or the multi-center phase 3 study.

Subjects who meet the general inclusion/exclusion criteria will be approached regarding their participation. Subjects who sign informed consent will be enrolled and assigned a unique subject identification number. Subjects will then be formally evaluated for eligibility through the performance of screening visit procedures. More than one visit may be necessary to complete all of the screening procedures. The two participating centers will accrue subjects over a 24 month period and will treat a total of 10 study subjects. No one center will treat more than 12 subjects.

Figure 1: Study Design Schema.

## 4.1 Study Endpoints

### 4.1.1 Primary Endpoint

The primary endpoint for this study is the proportion of **insulin-independent** subjects at day 75 ( $\pm 5$  days) following the first islet transplant.

### 4.1.2 Secondary Endpoints

The key secondary endpoint is the proportion of subjects with an HbA1c  $<7.0\%$  AND free of severe hypoglycemic events from Day 28 to Day 365, inclusive, after the first islet transplant.

The other secondary endpoint is the proportion of subjects with an HbA1c  $<7.0\%$  AND free of severe hypoglycemic events from Day 28 to Day 365, inclusive, after the final islet transplant.

#### 4.1.2.1 SECONDARY EFFICACY ENDPOINTS

At  $75 \pm 5$  days following the first islet transplant and following each subsequent islet transplant:

- The percent reduction in insulin requirements
- HbA1c
- Mean amplitude of glycemic excursions (MAGE)
- Glycemic lability index (LI)
- Ryan hypoglycemia severity (HYPO) score
- Basal (fasting) and 90-min glucose and c-peptide derived from the mixed-meal tolerance test (MMTT)
- $\beta$ -score
- C-peptide: (glucose X creatinine) ratio
- Acute insulin response to glucose (AIRglu), insulin sensitivity, and disposition index (DI) derived from the insulin-modified frequently-sampled IV glucose tolerance (FSIGT) test
- Glucose variability and hypoglycemia duration derived from the continuous glucose monitoring system® (CGMS)
- Quality of life (QOL) measures

If a third transplant occurs less than 75 days after the second transplant, the 75 day endpoint data for the second transplant will not be collected.

At  $365 \pm 14$  days following the first and final islet transplant:

- The percent reduction in insulin requirements
- HbA1c
- MAGE
- LI
- Clarke score
- HYPO score
- Basal (fasting) and 90-min glucose and c-peptide (MMTT)

- $\beta$ -score
- C-peptide: (glucose X creatinine) ratio
- AIRglu insulin sensitivity, and disposition index (DI) derived from the FSIGT test
- Glucose variability and hypoglycemia duration derived from the continuous glucose monitoring system® (CGMS)
- QOL measures
- The proportion of subjects receiving a second islet transplant
- The proportion of subjects receiving a third islet transplant
- Rate of favorable outcome at each center preparing islets (rate of subjects with an HbA1c < 7.0% and free of severe hypoglycemic events)

Secondary efficacy endpoints measured at  $365 \pm 14$  days following the final islet transplant will include the change in the above measures from the results obtained at  $75 \pm 5$  days following the final islet transplant.

At two years (730+14 days) following the final islet transplant:

- The percent change from baseline insulin requirements
- The number of severe hypoglycemic events from 28 days to two years
- HbA1c
- Clarke score
- Basal (fasting) and 90-min glucose and c-peptide (MMTT)
- $\beta$ -score
- C-peptide: (glucose • creatinine) ratio
- CGMS
- QOL

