#### 9.1.2.6 B-SCORE: A COMPOSITE INDEX OF POST-TRANSPLANT GRAFT FUNCTION

The  $\beta$ -score will be determined from the HbA1c, insulin requirements, fasting (basal) glucose, and stimulated c-peptide as developed by Ryan et al. The score may range from 0 (no graft function) to 8, with all subjects reported with a score of 8 also having 90-minute glucose levels during a MMTT that are  $\leq 10.0$  mmol/L (180 mg/dL), indicative of excellent graft function.

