#### **10.2.2 Secondary Endpoints**

Secondary endpoints are defined in section 4.1.2. There are a very large number of secondary endpoints so there will be no adjustment for multiplicity. We will not impute values for secondary endpoints but will conduct a sensitivity analysis to determine the potential magnitude of the contributions of the missing values. Details of the sensitivity analysis will be included in the SAP.

Analysis of secondary endpoints will use methods similar to those defined for the primary outcome. When the endpoint is a proportion such as patients achieving insulin independence at one year after completing their first islet transplant then the observed rate will be used as the point estimate and an exact 95% binomial confidence interval will be reported. Continuous variables will be treated in a similar fashion. If the necessary normality assumption is valid then the sample mean will be used as the point estimate and the usual 95% normal confidence intervals will be computed. Where the normality assumptions are not valid and an appropriate transform will achieve normality then the inverse of the mean of the transformed data will be used as the point estimate and the inverse of the endpoints for a standard 95% confidence interval for the transformed mean will be reported for the confidence interval. If no valid

transformation can be found then we will use the bootstrap method to construct a point estimate and a 95% confidence interval.

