**Appendix 2: Continuation of Appendix 1 Schedule of Events (Subjects with Subsequent CIT Transplants)**

Subjects who receive a subsequent islet transplant should continue their study visits according to this Schedule of Events until one year (365 +/- 5 days) after the final islet transplant. Additional visits - outlined in Appendix 3 - will also need to be completed after each subsequent transplant. After day 365 post final transplant, subjects should stop following this schedule, and complete the follow-up visits outlined in Appendix 4: *Schedule of Events for 1-Year Additional Follow-Up*.

Time points (in days relative to 1 st transplant)	392	420	448	476	504	532	560	588	616
Visit Number	22	23	24	25	26	27	28	29	30
Visit Windows (in days)	±5	±5	±5	±5	±5	±5	±5	±5	±5
Equivalent Week	W56	W60	W64	W68	W72	W76	W80	W84	W88
GENERAL ASSESSMENTS									
Physical Exam			X			X			X
QOL			X			X			X
AE/Hypo Event/Toxicity Assessment	X	X	X	X	X	X	X	X	X
LOCAL LABORATORY ASSESSMENTS									
CBC (WBC + Diff & Plat)			X			X			X
Chemistry 			X			X			X
Lipids			X			X			X
Pregnancy test (WOCBP) 	X	X	X	X	X	X	X	X	X
CENTRAL LABORATORY ASSESSMENT									
HbA1c			X			X			X
Fasting serum glucose & c-peptide & serum creat 	X	X	X	X	X	X	X	X	X
90 min  c-peptide/glucose (MMTT) 			X			X			X
Atherogenic Profile 	1 year post-final transplant								
LOCAL METABOLIC ASSESSMENTS									
BSR eCRFs 			X			X			X
CALCULATED METABOLIC ASSESSMENTS									
MAGE			X			X			X
LI			X			X			X
Clarke Score						X			
HYPO			X			X			X

Time points (in days relative to 1 st transplant)	392	420	448	476	504	532	560	588	616
Visit Number	22	23	24	25	26	27	28	29	30
Visit Windows (in days)	±5	±5	±5	±5	±5	±5	±5	±5	±5
Equivalent Week	W56	W60	W64	W68	W72	W76	W80	W84	W88
CALCULATED METABOLIC ASSESSMENTS (continued)									
Beta Score			X			X			X
C-peptide (glucose X creatinine) ratio	X	X	X	X	X	X	X	X	X
IMMUNOSUPPRESSION LEVELS									
Belatacept trough levels 	X	X	X	X	X	X	X	X	X
MECHANISTIC ASSAYS									
Alloantibodies 			X			X			X
Autoantibodies 			X			X			X
Immunogenicity samples 						X			
ARCHIVED SAMPLES									
Serum			X			X			X
Plasma			X			X			X

 EBV by PCR should only be done post-randomization if reactivation is suspected.

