
Time point (Equivalent weeks after 'Day 365 post final transplant' visit)	W4 (AY)	W8 (AY)	W12 (AY)	W16 (AY)	W20 (AY)	W24 (AY)	W28 (AY)	W32 (AY)	W36 (AY)	W40 (AY)	W44 (AY)	W48 (AY)	W52 (AY)	Y2  (AY)
Visit Number (relative to final islet transplant)	51	52	53	54	55	56	57	58	59	60	61	62	63	64
Visit Window (specified in days)	±5	±5	±5	±5	±5	±5	±5	±5	±5	±5	±5	±5	±5	±30
GENERAL ASSESSMENTS														
Physical Exam						X							X	X
Telephone Consult			X							X				
QOL													X	X
AE /Hypoglycemic Events/Toxicity Assessment			X			X				X			X	X
LOCAL LABORATORY ASSESSMENTS														
CBC (WBC + Diff & Plat)			X			X				X			X	
Chemistry 			X			X				X			X	
Lipids						X							X	
Pregnancy test (WOCBP) 	X	X	X	X	X	X	X	X	X	X	X	X	X	
CENTRAL LABORATORY ASSESSMENTS														
First morning spot urine 						X							X	
GFR													X	
HbA1c			X 			X				X 			X	X
90-min c-pep/glucose (MMIT) 						X							X	X
Atherogenic Profile													X	
LOCAL METABOLIC ASSESSMENTS														
Glycemic Stability (CGMS) 													X	X

 Two years post initial transplant.

 Also collect as necessary to confirm graft failure. Do not collect after graft failure is confirmed.

Time point (Equivalent weeks after 'Day 365 post final transplant' visit)	W4 (AY)	W8 (AY)	W12 (AY)	W16 (AY)	W20 (AY)	W24 (AY)	W28 (AY)	W32 (AY)	W36 (AY)	W40 (AY)	W44 (AY)	W48 (AY)	W52 (AY)	Y2  (AY)
Visit Number (relative to final islet transplant)	51	52	53	54	55	56	57	58	59	60	61	62	63	64
Visit Window (specified in days)	±5	±5	±5	±5	±5	±5	±5	±5	±5	±5	±5	±5	±5	±30
CALCULATED METABOLIC ASSESSMENTS														
Clarke Score													X	
IMMUNOSUPPRESSION LEVELS														
Belatacept Trough Levels	X	X	X	X	X	X	X	X	X	X	X	X	X	
MECHANISTIC ASSAYS														
Autoantibody						X							X	
MECHANISTIC ASSAYS (Cont'd)														
Alloantibody						X							X	
Immunogenicity Samples													X	X

 Since belatacept is infused every 28 days, an additional infusion visit will be required during the second year. Since the timing is dependent on final transplant date, this visit can be shifted as needed.

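### Two of the listed two-year endpoints, percent change in insulin requirements and the β-score, have no scheduled insulin record behind them

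*Protocol*

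**What the plan says.** Section 4.1.2.1 gives nine items under the lead-in "At two years (730+14 days) following the final islet transplant". The first is "The percent change from baseline insulin requirements"; the β-score is also on the list. Section 9.1.2.6 states that the β-score "will be determined from the HbA1c, insulin requirements, fasting (basal) glucose, and stimulated c-peptide".

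In Appendices 1, 2 and 3 insulin requirements reach the database on the Blood Sugar Record eCRF, which footnotes describe as compiled from diary logs, glucometer downloads and insulin requirements. Appendix 2 is followed "until one year (365 +/- 5 days) after the final islet transplant". After that, section 7.5 moves subjects to Appendix 4, whose columns are headed "Time point (Equivalent weeks after 'Day 365 post final transplant' visit" and end with week 52 (± 5 days) and a separate Y2 visit (± 30 days). One footnote numbered 1 in Appendix 4 defines Y2 as "Two years post initial transplant". A second footnote with the same number describes an extra infusion visit whose timing depends on the final transplant and may be shifted.

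Section 2.2 measures success as "the proportion of patients attaining and maintaining insulin independence after receiving a maximum of 3 islet transplants". Section 10.2.2 refers to section 4.1.2 for the secondary endpoints, then uses as its example "patients achieving insulin independence at one year after completing their first islet transplant".

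**The concern.** An endpoint needs a visit, a form and a window that agree. For the two insulin-based endpoints the form is missing in the year that matters. An analysis plan can decide how to summarise data, but it cannot supply doses that were never captured, and a week of insulin use is hard to reconstruct afterwards. With 10 subjects, uneven retrieval from diaries would leave little to summarise and no assurance that those retrieved represent the rest.

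Two lesser mismatches sit beside this. The two-year window, read literally, opens one day after the visit meant to serve it. And the success measure of the secondary objective does not appear in the endpoint list, so it has neither a time point nor a formal place in the analysis.

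**Working it through.** **1. Data source for each two-year item.** Week 52 of Appendix 4 is the visit closest to two years after the final transplant.

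| Two-year item (4.1.2.1) | Source at week 52 of Appendix 4 |
|---|---|
| Percent change in insulin requirements | None for the follow-up value; baseline is on the Blood Sugar Record in Appendix 1 |
| β-score | HbA1c and MMTT scheduled; insulin component missing |
| C-peptide ratio | No row, but computable: basal glucose and c-peptide from the MMTT (9.1.2.5), creatinine from the chemistry panel |
| HbA1c, MMTT values, Clarke score, CGMS, QOL | Scheduled |
| Severe hypoglycemic events | Assessed |

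Two of nine items therefore lack a scheduled source, and both lack the same thing.

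**2. Other places the insulin dose might come from.**
- Section 9.1.2.1 has subjects keep insulin diaries and gives no end date, but section 9.1.2 places the timing of the metabolic assessments in Appendices 1 to 3, and no Year-2 form captures the diary.
- Appendix 5 applies to subjects who stop treatment, whom section 5.7.2 keeps in the intent-to-treat analysis. Its two-years-after-last-transplant contact covers only serious adverse events, hypoglycemic events and QOL. HbA1c and the MMTT c-peptide are timed from the initial transplant.
- The follow-on protocol CIT08 records insulin use, but if screening falls within 90 days it takes the value from the final parent visit, which is where CIT04 schedules none.

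**3. Window.** Inputs: endpoint window 730+14 (section 4.1.2.1); anchor visit Day 365; week 52 ± 5 days (Appendix 4).
- Nominal week-52 day: 365 + 52 × 7 = 729.
- Permitted days: 729 ± 5 = 724 to 734, which is 11 days.
- Inside 730 to 744: 730 to 734, which is 5 of 11. Too early: 724 to 729, which is 6 of 11 and includes the target day.

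The anchor visit has its own window: ± 5 days in Appendix 2, ± 14 in Appendix 3. Counting every combination of permitted days (a count, not a probability):

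| Anchor | Week-52 range | Inside 730–744 | Inside 716–744 (730 ± 14) |
|---|---|---|---|
| 365 | 724–734 | 5/11 (45%) | 11/11 |
| 365 ± 5 | 719–739 | 55/121 (45%) | 121/121 |
| 365 ± 14 | 710–748 | 144/319 (45%) | 288/319 (90%) |

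**4. Whether the Y2 visit can stand in.** If Y2 is timed from the initial transplant, a single-transplant subject has 730 ± 30 = 700 to 760, which spans the endpoint window. For a final transplant at Day 85, Y2 falls nominally at 730 − 85 = 645 days after it. For one at about Day 243 (8 months, taken as 243 days), it falls at 730 − 243 = 487. Adding 30 days gives 675 and 517, both short of 716. If Y2 is timed from the final transplant the difficulty goes. The two footnotes do not settle which applies.

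**5. Insulin independence after the final transplant.** The Study Definitions need HbA1c, fasting glucose, an MMTT and 7 days of glucose and insulin readings. Appendix 3 schedules all of these at Days 75 and 365 after a subsequent transplant, and Appendix 1 does so after the first. The proportion can be derived to one year after the final transplant; it is simply not listed in section 4.1.2.

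**The case against.** The strongest reply is that little is truly lost. Section 5.6 treats insulin-use recording as a subject's duty and section 9.1.2.1 requires diaries, so doses may exist at the sites. That stands, and it limits the finding to the absence of scheduled capture. A reader might infer that two-year results as a whole cannot be produced, or that no subject could have either insulin-based endpoint. The documents do not support this: seven of the nine items are covered, and a subject with confirmed graft failure could arguably be given a β-score of 0, the value section 9.1.2.6 attaches to no graft function.

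On the window, the other timed windows in section 4.1.2.1 use ±, so 730+14 is probably a misprint. On the ± reading the mismatch largely vanishes. A reader might infer that on-time visits would lose their data, but the protocol states no rule discarding out-of-window values.

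On section 2.2, a reader might infer that maintenance of insulin independence can never be estimated. To one year after the final transplant it can; only maintenance into the second year lacks scheduled insulin data. Nor does the objective's reference to calcineurin inhibitors oblige the protocol to separate subjects given tacrolimus under section 5.2.3. That is an analysis preference which may sit in the statistical analysis plan.

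**Conclusion.** The point holds for two named endpoints. As scheduled, percent change in insulin requirements and the β-score at two years after the final transplant have no planned insulin record, in Appendix 4 or in Appendix 5, for any of up to 10 subjects. This assumes that neither the Manual of Procedures nor another document not shown adds the record. The primary endpoint and the one-year endpoints are unaffected.

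The window mismatch is minor and rests on reading 730+14 literally. The Y2 footnotes conflict and must be reconciled. The section 2.2 measure is an unlisted endpoint without a time point, and the example in section 10.2.2 is likewise absent from the list that section cites. These are reconciliation items, best dealt with in the same amendment.

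**What to change.** 1. Add the Blood Sugar Record eCRF (7 days of glucose and insulin) to week 52 of Appendix 4, the visit that serves two years after the final transplant.
2. Add an insulin-use record to the two-years-after-last-transplant contact in Appendix 5. Derive the β-score wherever its components are available, and say so.
3. Write the two-year window as 730 ± 14 days in the synopsis and section 4.1.2.1. Reconcile the two Appendix 4 footnotes numbered 1, so that the anchor of the Y2 visit is unambiguous.
4. List in section 4.1.2.1 the proportion insulin independent, by the Study Definitions, at 75 ± 5 and 365 ± 14 days after the final transplant, and state how the two together address section 2.2. Align the example in section 10.2.2 with the list. Handle missing values by the sensitivity analysis in section 10.2.2, which rules out imputation for secondary endpoints; do not count unassessed subjects as failures.

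The cost is one existing form at one existing visit, one item at an existing contact, and some wording. Item 4 needs no new data collection.
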